**F. Risk/benefit assessment:**

**Physical risk:** Blood tests usually result in some discomfort during the blood draw and may result in mild bruising at the site of the blood draw. Fasting before blood testing may result in some discomfort and feeling hungry. Some people experience dizziness or feel faint after having blood drawn. The medical tape used to attach the monitor to the thigh may cause redness or stick to leg hair.

**Psychological risk:** It is possible that wearing activity monitors, keeping a diary, or filling out questionnaires will be tiring or annoying.

**Social & Economic risk:** We do not foresee any social or economic risk to participating in the study.

**Potential benefit of participating in the study**

- a. Individual subject: The participant may learn about his/her own activity and sedentary habits and they may learn strategies to make them healthier. This information may benefit health and well-being.
- b. Study Population: We do not expect the population from which the subject is drawn to benefit in any particular way.
- c. Science, society, and humanity in general: The new information that will be obtained may benefit future patients by providing new insights into healthy aging and prevention of Alzheimer's disease or Mild Cognitive Impairment (MCI).

**G. Location where study will be performed:** Participants will visit the Clinical Translation Science Unit in Fairway, KS for study visits. Activity monitoring, home visits, and telephone calls will take place in the participant's home and community environment. Data will be stored at the KU Alzheimer's Disease Center and the PI's research lab at the University of Kansas in Lawrence.

**H. Collaboration (with another institution, if applicable): NA**

**I. Single IRB Review for a Multi-site study (if applicable): NA**

**J. Community-Based Participatory Research (if applicable): NA**

**K. Personnel who will conduct the study, including:**

1. Indicate, by title, who will be present during study procedure(s): Study Coordinator, Research Assistants
2. Primary responsibility for the following activities, for example:
  - a. Determining eligibility: Study Coordinator, PI, Research Assistants
  - b. Obtaining informed consent: Study Coordinator, Research Assistants
  - c. Providing on-going information to the study sponsor and the IRB: NA
  - d. Maintaining participant's research records: Study Coordinator, Research Assistants, PI

- e. Completing physical examination: N/A
- f. Taking height, weight: CTSU staff
- g. Drawing / collecting laboratory specimens: CTSU staff
- h. Performing / conducting tests, procedures, interventions, questionnaires: Study Coordinator, Research Assistants
- i. Completing study data forms: Study Coordinator, Research Assistants
- j. Managing study database: PI, Research Assistants

## **L. Assessment of Subject Safety and Development of a Data and Safety Monitoring Plan**

1. Elements of the plan include:
  - a. **Persons/groups who will review the data:** CTSU and research staff
  - b. **Data/events that will be reviewed:** Reports from participants to study staff will be recorded during study visits and telephone calls.
  - c. **Frequency of review:** quarterly
  - d. **Types of analyses to be performed:** assess frequency and severity of reported events
  - e. **Safety-related triggers that would cause the PI to stop or alter the study:** No anticipated safety-related events

Eligibility criteria screen for health risks prior to study enrollment, and we will immediately report to PI any adverse events. Postprandial glucose and insulin testing is the only procedure that increases risk to participants above the risks in daily life and that portion will be continuously monitored in the CTSU. Home visits and telephone calls to study participants from study staff occur frequently during the study period to monitor any additional unforeseen problems. We will record and review any reported adverse events for severity. If deemed, severe, participation will be discontinued.

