Cardiorespiratory fitness changes that only occur with moderate or vigorous aerobic exercise may not be essential for improving brain health and cognition, as demonstrated by studies of activities that do not robustly improve fitness (Tai Chi, resistance training, Wii fit), but still show improvements in brain health and cognition. Even low intensity, non-exercise activity is associated with reduced risk of cognitive decline and healthier cardiometabolic measures. In fact, non-exercise activity accounts for the majority of daily activity, while exercise accounts for only 2-5%. More evidence is needed to determine whether reductions in sitting time are sufficient to produce changes in cognitive performance and neuroanatomy as seen in aerobic exercise interventions.

A recent meta-analysis reports that interventions targeting sedentary behavior can effectively reduce sitting time in adults (average 42 min/day), but few studies have evaluated whether these reductions result in clinically meaningful health outcomes. Furthermore, few interventions have been conducted in older adults. One intervention to reduce sitting time in older adults included one on one goal setting and individualized feedback on objectively derived sitting time. Participants successfully reduced sitting time, increased breaks in sitting, and increased light and moderate intensity activities. Our 12 week intervention

adds new elements to strengthen this design: 1) objective *postural* monitoring, 2) electronic reminders when sitting >30 minutes (real time reminders are more effective than education alone in reducing sitting), 3) assessment of insulin sensitivity and glycemic control which are sensitive to changes in sitting after a short duration.

The proposed intervention is ecologically valid—it can be done in any setting. It uses participants' goals and preferences to guide behavior changes instead of defining goals for them. The intervention is designed to break up bouts of prolonged sitting and replace sitting behavior with standing, light and moderate intensity activities (e.g., walking, household activities, and resistance exercise) which have been associated with improved cognitive performance among people at risk for AD.

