## **V. Data Analysis and Reporting**

### **Statistical and Data Analysis:**

**Data Analysis:** We will use a multi-level model to evaluate the change in our outcome variables across three time points. Level 1 is time of observation (baseline, mid-study, follow up). Level 2 is the individual (with or without MCI), and Level 3 is the level of the dyad. This model includes the non-independence in the estimation of the two members of the dyad as well as repeated observations for each individual. This model also allows us to compare whether individuals with MCI are equally or less responsive to the intervention than the study partners within the context of the dyadic relationship. Constraining estimates to be equivalent provides a test of the significance of the difference in the estimates between the MCI patients and the study partners. We are primarily interested in the change in outcome measures (listed below) from pre-intervention to post-intervention (i.e., is the intervention effective), thus we are testing for a growth model with an intercept change, indicating a mean change after the intervention, this type of model can estimate discontinuous processes with longitudinal data. With regard to the multiple time points, we hypothesize an improvement in outcomes from baseline to mid-point and a maintenance effect from mid-point to follow up. Outcomes are (1) average daily sitting time (2) number of sitting bouts >30 min (3) insulin and glucose, adjusting for baseline values and relevant covariates (disability status, medications, age, education, etc.). **Outcome:** Milestones for achieved **feasibility** include successful recruitment and retention of participants, 10% or less of technological failures, rate of participant concerns addressed by phone and at home visits, acceptability of the intervention to participants (measured by questionnaires HI3), and few adverse events. Effectiveness of the intervention will be evaluated based on change of moderate effect size in the average amount of time spent in sitting and duration of sitting bouts as demonstrated in previous studies. Two previous intervention studies reported a decline in sitting time of about 3 - 4%. We will use this range as our target for success.

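### Adverse events rest on unstructured participant reports, no risk from the added activity is named, and the "few adverse events" milestone has no number or denominator

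*Combined protocol and SAP*

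**What the plan says.** **Risk.** Section II.L says that "Postprandial glucose and insulin testing is the only procedure that increases risk to participants above the risks in daily life". Section II.F lists effects of the blood draw, fasting and adhesive tape, plus tiredness or annoyance from monitors, diaries and questionnaires. Neither section names a risk from moving more. Falls are mentioned nowhere in the documents.

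**What participants are asked to do.** Section I.B says the intervention is meant to "replace sitting behavior with standing, light and moderate intensity activities (e.g., walking, household activities, and resistance exercise", among other examples. Under II.E (Procedures), a wrist monitor vibrates after more than 30 inactive minutes. Participants are selected for being sedentary, and 15 of the 30 have MCI.

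**How events are found.** Under II.L, "Reports from participants to study staff will be recorded during study visits and telephone calls", and the planned analysis is to "assess frequency and severity of reported events". The entry for safety triggers reads "No anticipated safety-related events". The same section adds: "Home visits and telephone calls to study participants from study staff occur frequently during the study period to monitor any additional unforeseen problems". II.E sets out what the contacts cover: alerts and monitor wear, goals, barriers and acceptability. It describes no adverse-event question.

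**How safety is judged.** Section V includes "few adverse events" among the feasibility milestones. The Aim 1 lists in I.A and in Sample Size, Statistical Methods, & Power do not. By contrast, technological failures have a limit (10%) and a denominator (participants enrolled).

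**The concern.** The events that matter most for this intervention are those that standing up and moving more could bring: falls, dizziness on standing, new or worse pain. The plan neither names them nor says how staff will ask about them. The count therefore depends on how each staff member conducts a visit and on what a participant remembers, and half of the participants have cognitive impairment.

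The error runs one way. Missed events lower the count, and a low count is what the milestone rewards. Because the milestone has no number, nobody can say afterwards whether it was met.

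Section V says the pilot will support an application for a larger RCT. Tolerability of the added activity is something a feasibility study can describe for that trial, and this plan does not set it up to be measured.

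**Working it through.** The documents give no event rate, threshold or safety calculation, so there is no figure to reproduce. Three checks can be made.

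**1. Recall period.** From the start of the intervention, Table 2 places contacts at weeks 1, 2, 5, 8, 12 and 14 (HI1, TI1, HI2, TI2, HI3, V2). The gaps are 1, 3, 3, 4 and 2 weeks, so recall may have to reach back four weeks.

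**2. What a clean record can show.** If no participant out of n has an event and capture is complete, the one-sided 95% upper bound on the true share is 1 − 0.05^(1/n).
- n = 30: 1 − 0.05^(1/30) = 9.5%.
- n = 15 (one role): 1 − 0.05^(1/15) = 18.1%.

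These bounds reflect sample size, not the reporting method. If only a fraction c of affected participants is captured, the bound is divided by c. At an assumed c = 0.5 it becomes 9.5% / 0.5 = 19.0% for 30 and 18.1% / 0.5 = 36.2% for 15.

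**3. Whether capture can decide the milestone.** This is an illustration. Let p be the true share of participants with at least one event and c the share of those captured. Both are assumptions, as is reading "few adverse events" as two or fewer affected participants. The number recorded is taken as binomial with n = 30 and probability q = p × c, which treats the partners in a dyad as independent. Then P(2 or fewer) = Σ C(30,k) q^k (1 − q)^(30−k), for k = 0, 1, 2.

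| True share p (expected affected) | c = 100% | c = 75% | c = 50% | c = 25% |
|---|---|---|---|---|
| 5% (1.5) | 81% | 90% | 96% | 99% |
| 10% (3) | 41% | 61% | 81% | 96% |
| 20% (6) | 4% | 15% | 41% | 81% |
| 30% (9) | 0.2% | 2% | 15% | 61% |

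Worked cell, p = 10% and c = 100%: 0.9^30 + 30 × 0.1 × 0.9^29 + 435 × 0.01 × 0.9^28 = 0.042 + 0.141 + 0.228 = 0.411.

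Across every row, weaker capture raises the chance of meeting the milestone. At a true share of 20%, the chance goes from 4% with full capture to 81% with quarter capture. At 5% the milestone is usually met whatever the capture. The table shows direction and sensitivity; it does not forecast event rates in this study.

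**The case against.** Several points on the other side are fair.

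- **Capture is not stated to be passive.** A reader might infer that events are counted only when participants volunteer them. The documents do not say so. II.L gives staff visits and calls the purpose of monitoring unforeseen problems, and adverse events go to the principal investigator immediately. The plan is silent on what staff ask. This stands, and it limits the point to unstructured capture.
- **The milestone does not pass automatically.** A reader might infer that it is met by default. Reported events are recorded and reviewed for severity, so a high count could fail it. The defect is that it is undefined and easily met.
- **An informant is at hand.** Partners live together, the caregiver is unimpaired, and the intervention is delivered to the dyad together. This makes partner reporting easy to add, but the plan does not say the partner will be asked about the person with MCI.
- **Other data may surface events.** Self-reported pain is a covariate, physical barriers are discussed, and participant concerns are counted. None of these is defined as safety data, and falls remain the clearest gap.
- **Risk may be low.** People who cannot stand or walk unassisted are excluded, and participants set their own goals. A reader might infer that the sole-procedure statement is false. Whether the added activity exceeds daily-life risk needs evidence outside the documents. What can be shown is that the risk sections do not address the activity at all.
- **Attribution is impossible.** The study has one group, so even a perfect count could not separate intervention effects from background events. This stands. Counts with intervals still help to plan the next trial.

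**Conclusion.** The point holds as a shortfall in measurement and definition. The plan has no standard safety question, event definition or stated partner report. Its risk sections are silent on the activity it promotes, and its safety milestone has no number or denominator and appears in section V but in neither Aim 1 list. The possible bias has one direction, towards meeting the milestone.

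The size of that bias cannot be derived from the documents. Any fall rate or capture fraction is an assumption and should be shown as a range, as in the table above. The upper bounds of 9.5% (0 of 30) and 18.1% (0 of 15) need no assumed event rate. They do need complete capture and, for the 30, independence between partners. The documents do not support the conclusion that harm is being missed or that the intervention is unsafe.

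This should be changed before enrolment because the remedy is cheap. It does not threaten the sitting-time or biomarker aims.

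**What to change.** 1. **Ask a fixed set of questions.** At each existing contact (HI1 to HI3, TI1 and TI2, V2, as labelled in Table 2), ask both partners about falls, dizziness and new or worse pain since the last contact. Ask the partner the same about the person with MCI. Write down what counts as an event.
2. **Describe the period before the intervention.** At HI1, ask the same set for a stated pre-intervention period. Four weeks would match the longest later gap. Use it as description only, because there is no control group.
3. **Define the milestone before enrolment.** Give "few adverse events" a number, a denominator and a time window (for example, whether events between HI3 and V2 count). Choose the number knowing that structured questions will find more events. Add the milestone to both Aim 1 lists.
4. **Report with intervals.** Give participants with at least one event out of 30, and out of 15 by role, with exact confidence intervals. The by-role intervals avoid dependence within dyads.
5. **Reconcile the risk statements.** II.F and II.L should be made consistent with the activity described in I.B and II.E. This is a request for consistency, not for any particular clinical rule.

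**Cost.** One form and about one minute per contact. With 6 contacts for each of 15 dyads, that is 6 × 15 = 90 contacts, or about 90 minutes in all. No visits are added. The downside is a higher recorded event count, which could make the milestone harder to meet.

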## **III. Subject Participation**

### **A. Recruitment:**

1. We will recruit and collect data from participants currently participating in the KU-ADC Registry. This is a large registry of well characterized patients that has demonstrated an excellent ability to identify, recruit, and characterize individuals with mild AD and healthy older adults and retain them for investigator initiated research studies. Participants with MCI have had a full physical and neurological examination and review of medical history as part of the Alzheimer's Disease Center Registry evaluation before being recruited into the present study. No subject who is eligible to participate based upon the inclusion/ exclusion criteria; desires to participate in this study; is eligible for the study will be denied based upon race, gender or ethnicity.
2. The study coordinator and/or research assistants will identify potential participants via chart review and telephone screening.
3. Recruitment letters will be mailed to potentially eligible participants. Copies of recruitment letter, website description, and pocket card for recruitment are attached. The pocket card is used as a tool for study coordinators to have handy information to inform participants they contact in person or over the phone about the study.

**B. Screening Interview/questionnaire:** As members of the KU Alzheimer's Disease Center Registry, potential participants have previous consented to being contacted for future research. During eligibility screening, the study coordinator or research assistants will contact potential participants by telephone. They must meet the inclusion/exclusion criteria given in Table 1. Clinical Dementia Rating scores will have been determined in a previous registry visit for those with MCI. Additional questions will include work/retirement status, availability of a willing study partner, able to stand or walk unassisted, adequate English language, auditory, and visual capacity, adhesive allergy, current uncontrolled Type 2 diabetes, and willingness to change sitting behavior. To evaluate eligibility for sedentary behavior, we will use the MOST questionnaire which is shown in Appendix II below.

**C. Informed consent process and timing of obtaining of consent**

- 1 The study coordinator who is experienced in working with participants from the KU-ADC participant Registry, will give subjects detailed and comprehensive information about the study and obtain their written consent.
- 2 For all study participants, consent forms will be reviewed and signed in a private, clinic room at the Alzheimer's Disease Center or CTSU/GCRC. The potential subjects will be given the consent form to fully review prior to signing.
- 3 Both caregivers and persons with cognitive impairment who are potential participants for the study will be given details about the study as stated in the consent form. Both the caregiver and the person with impairment will be asked to describe what they will do to participate in the study, the risks and benefits of participation, and what they would do if they decided they wanted to discontinue participation in the study. Their ability to relay back key information about the study will be used to determine whether they have capacity for consent. We will not enroll participants who are unable to consent for themselves. We will obtain written consent from all participants.

**D. Alternatives to Participation:** Participation in the study is entirely voluntary. Participants may withdraw at any time and no care or services will be denied on the basis of participation or lack thereof.

**E. Costs to Subjects:** There are no costs to participants.

**F. How new information will be conveyed to the study subject and how it will be documented:** Participants will be notified verbally and in writing if any new information is determined that might alter the participant's wish to participate in research.

**G. Payment, including a prorated plan for payment:** Participants will not be paid to participate in the study. Upon study completion they will be able to keep their wrist worn activity monitors (value about \$100).

**H. Payment for a research-related injury:** If participants have research-related injuries, they will be provided treatment at the usual charge. Treatment may include first aid, emergency care and follow-up care, as needed. Claims will be submitted to their health insurance policy, government program, or other third party, but they will be billed for the costs that are not covered by the insurance.

## **IV. Data Collection and Protection**

### **A. Data Security**

**Data Sharing, Management, & Quality Control:** We have signed a formal data use agreement specifying the terms of data use and protection. Data collection and sharing for this project was funded by the KUADC (NIH P30AG035982). KUADC has a designated Data Management Core that provides support for data collection, management and secure storage. All data are entered on standardized forms during the clinical visits and entered into a central database. Data are doubly entered to minimize data entry errors. Upon completion, we conduct logic, edit, and range checks. Queries are sent to the study coordinator for resolution. Data are downloaded and locked in a secure dataset. The database is backed up in an off-site location. Data security is ensured by managing all data on a secure server that has role-based access that is password protected. All files that are modified are backed up daily, with complete backups of the server on a weekly basis. Confidentiality is strictly safeguarded by HIPAA-compliant standards and all data are stored in a HIPAA compliant manner. All paper records will be kept in locked files in the research offices to which only our research personnel have access and filed by number in accordance with professional standards of privileged information. Any information on the subjects which may be shared will only be identifiable through a code number and will not have any personal information attached. Empathetic and professional staff mitigates risk of embarrassment. There are no plans to have ongoing third party monitoring.

**B. Sample / Specimen Collection:** At the CTSU, fasting and postprandial glucose and insulin will be collected to measure glycemic control and insulin sensitivity. An IV catheter will be placed for sampling by a nurse. Fasting baseline blood will be drawn. Subjects will then consume a liquid mixed meal (Ensure drink containing 57% carbohydrate, 28% fat, and 15% protein). Blood will then be collected at 15, 30, 45, 60, 90, and 120 minutes after consumption of the drink. Glucose will be measured in all samples immediately after collection with a glucose analyzer (YSI 2300 Stat plus). Remaining blood will be processed with centrifugation and serum separated and stored at -80 until time of analysis. Insulin will be measured in serum using Enzyme-Linked Immunosorbent Assay (ELISA; Alpco Diagnostics). Samples will be stored in a secure location within the CTSU to which only CTSU and study staff have access. The samples will not be shared outside this research, but will be sent to an external site for processing.

